Power Frequency H-field IEC 61000-4-8	50 and 60 Hz, 30 A/m, x-, y-, and z- axes	50 and 60 Hz, 30 A/m, x-, y-, and z- axes

 BD	Document Type: Global Clinical	Page No: 52 of 59
	Title: Clinical Investigation Plan Study ID: UCC-23AC023	Version No: 1.0

Template GFM-10095B

Voltage Dips, Interrupts IEC 61000-4-11	0% UT; 0,5 cycle At 0°, 45°, 90°, 135°, 180°, 225°, 270° and 315° 0% UT; 1 cycle 70% UT; 25/30 cycles Single phase: at 0° 0% UT; 250/300 cycle	0% UT; 0,5 cycle At 0°, 45°, 90°, 135°, 180°, 225°, 270° and 315° 0% UT; 1 cycle 70% UT; 25/30 cycles Single phase: at 0° 0% UT; 250/300 cycle
Proximity magnetic fields IEC 61000-4-39	8 A/m, CW Modulation @ 30kHz 65 A/m, 2.1 kHz Pulse [contact] 7.5 A/m, 50 kHz Pulse [contact]	8 A/m, CW Modulation @ 30kHz 65 A/m, 2.1 kHz Pulse [contact] 7.5 A/m, 50 kHz Pulse [contact]
Proximity fields from RF wireless communications equipment IEC 61000-4-3: Complies, refer below IEC 60601-1-2: Table 9 (please refer the below table in page 16).		

IEC 60601-1-2: Table 9 – Test specifications for ENCLOSURE PORT IMMUNITY to RF wireless communications equipment				
Test frequency (MHz)	Band ^{a)} (MHz)	Service ^{a)}	Modulation	IMMUNITY TEST LEVEL (V/m)
385	380 to 390	TETRA 400	Pulse modulation ^{b)} 18 Hz	27
450	430 to 470	GMRS 460, FRS 460	FM ^{c)} ± 5 kHz deviation 1 kHz sine	28
710	704 to 787	LTE Band 13, 17	Pulse modulation ^{b)} 217 Hz	9
745				
780				
810	800 to 960	GSM 800/900, TETRA 800, iDEN 820, CDMA 850, LTE Band 5	Pulse modulation ^{b)} 18 Hz	28
870				
930				
1 720	1 700 to 1 990	GSM 1800; CDMA 1900; GSM 1900; DECT; LTE Band 1, 3, 4, 25; UMTS	Pulse modulation ^{b)} 217 Hz	28
1 845				
1 970				
2 450	2 400 to 2 570	Bluetooth, WLAN, 802.11 b/g/n, RFID 2450, LTE Band 7	Pulse modulation ^{b)} 217 Hz	28
5 240	5 100 to 5 800	WLAN 802.11 a/n	Pulse modulation ^{b)} 217 Hz	9
5 500				
5 785				

	Document Type: Global Clinical Title: Clinical Investigation Plan Study ID: UCC-23AC023	Page No: 53 of 59
		Version No: 1.0

Template GFM-10095B

The PureWick™ Urine Collection System bears the following symbols:

 Packaging Unit	 Non-sterile	 Class II	 Humidity Limitation
 Catalog Number	 Do not use if package is damaged and consult Instructions for Use.	 Type BF Applied Part	 Atmospheric Pressure Limitation
 Lot Number	 Caution	 Refer to Instruction Manual/Booklet	 Caution, Risk of Electric Shock
 Serial Number	 Manufacturer	 Temperature Limit	IP21 Degree of Protection against harmful ingress of water and particulate matter.
 Use By date	 Date of Manufacture	 Certified To CSA STD C22.2 NO. 60601-1 Conforms To Medical Electrical Equipment STDS 60601-1, 60601-1-6 and 60601-1-11	 M.E.E.

 **WARNING:** This product¹ can expose you to lead, which is known to the State of California to cause cancer and birth defects or other reproductive harm. For more information go to: <https://www.P65Warnings.ca.gov>.

[figure not shown]
[figure not shown]
¹ The product is the A/C Power Cord.

IP21 Classification – Protection of equipment against ingress of solid foreign objects which are greater than or equal to 12.5mm in diameter and protection of equipment against harmful effects of ingress from vertically dripping water.

	Document Type: Global Clinical Title: Clinical Investigation Plan Study ID: UCC-23AC023	Page No: 54 of 59
		Version No: 1.0

Template GFM-10095B

[figure not shown]
[figure not shown]
26.4 Appendix 4 - Participant - Perception of Wetness Questionnaire (Both Male & Female)

Participant Number:	Device:					
	 PureWick Male External Catheter	 PureWick Flex Female External Catheter				
After HCP Placement Void						
		Extremely wet	Very wet	Somewhat wet	Slightly wet but acceptably dry	Dry (not at all wet)
	Question	1	2	3	4	5
1	On a scale of 1-5 where 1 is 'Extremely wet' and 5 is 'Dry, (not at all wet)', how wet or dry did you feel after your urination (pee)?					
1a	If you selected 1, 2 or 3, please provide comments to tell us why you answered as you did (free text)					
	Question	Yes	No			
2	Did you feel leakage while urinating during use of the device?					
After Self-Placement Void						
		Extremely wet	Very wet	Somewhat wet	Slightly wet but acceptably dry	Dry (not at all wet)
	Question	1	2	3	4	5
1	On a scale of 1-5 where 1 is 'Extremely wet' and 5 is 'Dry, (not at all wet)', how wet or dry did you feel after your urination (pee)?					
1a	If you selected 1, 2 or 3, please provide comments to tell us why you answered as you did (free text)					
	Question	Yes	No			
2	Did you feel leakage while urinating during use of the device?					

	Document Type: Global Clinical Title: Clinical Investigation Plan Study ID: UCC-23AC023	Page No: 55 of 59
		Version No: 1.0

Template GFM-10095B

26.5 Appendix 5 – Participant – Ease of use Questionnaire (Both Male & Female)

Participant Number:	Device:					
	 PureWick Male External Catheter	 PureWick Flex Female External Catheter				
After Self-Placement Void						
		Very difficult	Somewh at difficult	Average difficulty	Somewh at easy	Very easy
	Question	1	2	3	4	5
1	On a scale of 1-5, where 1 is Very difficult, and 5 is Very Easy, How easy was the placement of the device?					
2	On a scale of 1-5, where 1 is Very difficult, and 5 is Very Easy, How easy was the removal of the device?					
The following questions are applicable for FEMALE participants only.						
Please respond to the following questions regarding the PureWick™ Flex Female External Catheter on a scale of 1-5, where 1 is Strongly Disagree, and 5 is Strongly Agree.						
		Strongly Disagree	Disagree	Neutral	Agree	Strongly Agree
	Question	1	2	3	4	5
3	I was able to connect the device PureWick™ Flex FEC tubing to the suction tubing on the PureWick™ Urine Collection System					
3a	If you selected 1, 2 or 3, please provide comments to tell us why you answered as you did (free text).					
4	I was able to locate the vent hole on the PureWick™ Flex FEC and make sure it was not blocked.					
4a	If you selected 1, 2 or 3, please provide comments to tell us why you answered as you did (free text).					

	Document Type: Global Clinical	Page No: 56 of 59
	Title: Clinical Investigation Plan Study ID: UCC-23AC023	Version No: 1.0

[figure not shown]
[figure not shown]
Template GFM-10095B

5	I would be able to tell if the PureWick™ Flex FEC came out of place.						
5a	If you selected 1, 2 or 3, please provide comments to tell us why you answered as you did (free text).						
6	I would be able to tell if the PureWick™ Flex FEC was in the correct orientation (i.e. tubing pointed toward the belly button).						
6a	If you selected 1, 2 or 3, please provide comments to tell us why you answered as you did (free text).						
7	I was able to curve the PureWick™ Flex FEC to fit my body.						
7a	If you selected 1, 2 or 3, please provide comments to tell us why you answered as you did (free text).						

	Document Type: Global Clinical Title: Clinical Investigation Plan Study ID: UCC-23AC023	Page No: 57 of 59
		Version No: 1.0

Template GFM-10095B

[figure not shown]
[figure not shown]
26.6 Appendix 6 – Participant Comfort Questionnaire (**Both Male and Female**)

Participant Number:	Device:					
	 PureWick Male External Catheter					
	 PureWick Flex Female External Catheter					
After Completion of All Voids						
Please respond to the following questions regarding device comfort on a scale of 1-5, where 1 is Very Uncomfortable, and 5 is Very Comfortable						
		Very uncomfortable	Uncomfortable	Neither Comfortable nor Uncomfortable	Comfortable	Very Comfortable
	Question	1	2	3	4	5
1	How comfortable was the placement of the PureWick™ External Catheter?					
2	How comfortable was the device while you were voiding ?					
3	How comfortable was the removal of the PureWick™ External Catheter?					
		Very Unlikely	Unlikely	Neither Likely nor Unlikely	Likely	Very Likely
	Question	1	2	3	4	5
4	On a scale of 1 to 5 where 1 is very unlikely and 5 is very likely, how likely would you be to recommend the PureWick™ External Catheter to someone else?					

	Document Type: Global Clinical Title: Clinical Investigation Plan Study ID: UCC-23AC023	Page No: 58 of 59
		Version No: 1.0

Template GFM-10095B

[figure not shown]
[figure not shown]

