4.2 Rationale

The purpose of this study is to understand if external catheters are an effective alternative in the adolescent population in both male and female adolescents in the setting where the external catheter is placed by a healthcare professional as well as in the outpatient or home setting where the external catheter is self-placed or placed by guardian/parent, and to provide data to support potential labeling for an expanded population use. Specifically, the study will collect data about how the external catheters perform in terms of capture rate when participants are voiding after self-placement of the device, if the adolescent participant can use the device independently or with the help of a guardian/parent and collect any adverse events that are reported.

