Steps	Activity 4 (Removing the device)
4.1	
After the completion of the void the participant (or guardian/parent) or HCP (based off placement sequence) will carefully remove the device per the instructions for use.
 
 • For female participants, HCP will record if the device has dislodged after the void prior to device removal
4.2	The HCP will record whether they observed any urine leak from the device upon removal.

	Document Type: Global Clinical Title: Clinical Investigation Plan Study ID: UCC-23AC023	Page No: 18 of 59
		Version No: 1.0

Template GFM-10095B

4.3	The HCP will lift the catheter and tubing to make sure all the liquid flows into the canister.
4.4	The HCP will perform a skin integrity check and note any signs of irritation in the perineal area or adverse reactions. HCP will confirm if no signs or symptoms of irritation in the perineal area were noted.
4.5	The HCP will turn the PUCS suction OFF by flipping the black switch on the PUCS.
4.6	The used absorbent pad will be weighed by the HCP, and the value documented on the appropriate CRF. The canister (with lid) with urine will be weighed by the HCP and documented. The used catheter will be disconnected from the tubing and discarded.
4.7	The participant will be asked to complete all applicable questionnaires.
Steps	Activity 5 (Void #2)
5.1	After completion of void 1, the participant will be instructed to drink fluids in preparation for void 2.
5.2	Approximately 30 minutes after void 1 or when the participant feels the need to void again, the participant will proceed with void 2 (the participant will not use the same wetted device but a new clean device). Steps in Activities 1-4 will be repeated for the 2 nd void based off the placement sequence.
Steps	Activity 6 (After Completion of Both Voids)
6.1	Once the participant has completed both voids, the participant will be asked to complete the remaining required questionnaire.
6.2	Each HCP will complete the ease-of-use questionnaire after completing all study activities.

Questionnaires to be completed

Person to complete questionnaire	Questionnaire to complete	When to complete
Participant	Perception of wetness	After each void
Participant	Ease of use	After self-placement void
Participant	Comfort	After completion of all voids
Participant	IFU Evaluation	After self-placement void
HCP	Ease of use	After completion of all participants. Each HCP completes this questionnaire once per device.

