2.2.5 Secondary Endpoint 2 – Overall Comfort Score

Table 15 Participant Comfort Scale Survey

ITT

	PureWick Flex Female (N = xx)	PureWick Male (N = xx)
Questionnaire Completed		
Yes	n (%)	n (%)
No	n (%)	n (%)
How Comfortable was the Placement?		
1-Very Uncomfortable	n/N(%)	n/N(%)
2-Uncomfortable	n/N(%)	n/N(%)
3-Neither Comfortable Nor Uncomfortable	n/N(%)	n/N(%)
4-Comfortable	n/N(%)	n/N(%)
5-Very Comfortable	n/N(%)	n/N(%)
Mean(SD)	xx.x (xx.x)	xx.x (xx.x)
Median	xx.x	xx.x
Min-Max	xx-xx	xx-xx
How Comfortable was the Device While Voiding?		
1-Very uncomfortable	n/N(%)	n/N(%)
2-Uncomfortable	n/N(%)	n/N(%)
3-Neither Comfortable Nor Uncomfortable	n/N(%)	n/N(%)
4-Comfortable	n/N(%)	n/N(%)
5-Very Comfortable	n/N(%)	n/N(%)
Mean(SD)	xx.x (xx.x)	xx.x (xx.x)
Median	xx.x	xx.x
Min-Max	xx-xx	xx-xx
How Comfortable was the Removal of the External Catheter?		
1-Very uncomfortable	n/N(%)	n/N(%)
2-Uncomfortable	n/N(%)	n/N(%)
3-Neither Comfortable Nor Uncomfortable	n/N(%)	n/N(%)
4-Comfortable	n/N(%)	n/N(%)
5-Very Comfortable	n/N(%)	n/N(%)
Mean(SD)	xx.x (xx.x)	xx.x (xx.x)
Median	xx.x	xx.x
Min-Max	xx-xx	xx-xx
How Likely Would You Recommend the External Catheter to Someone Else?		
1-Very Unlikely	n/N(%)	n/N(%)
2-Unlikely	n/N(%)	n/N(%)
3-Neither likely Nor Unlikely	n/N(%)	n/N(%)
4-Likely	n/N(%)	n/N(%)
5-Very Likely	n/N(%)	n/N(%)

THIS SUBJECT MATTER IS RESTRICTED SOLELY FOR THE USE OF BECTON DICKINSON AND COMPANY AND ITS SUBSIDIARIES

	Title: UCC-23AC023 Statistical Analysis Plan Table shells	Page No. 23 of 33
	Study Title: UCC-23AC023 PureWick Adolescent Study CIP/CPSP Version: 1.0	Version No: 1.0

Template GFM-10082B

Mean(SD)	xx.x (xx.x)	xx.x (xx.x)
Median	xx.x	xx.x
Min-Max	xx-xx	xx-xx

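### Comfort is rated once after both voids, so it cannot be reported separately for HCP placement and for self or guardian/parent placement; asking after each void is a cheap improvement

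*Protocol*

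**What the plan says.** Protocol Section 7.1 gives each participant two voids, one with HCP placement and one with self-placement. A guardian or parent may step in only if the participant cannot or will not place the device. Section 7.3.1 randomises the order 1:1. Step 4.1 of Section 10.4 makes removal follow the same sequence.

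The timing table in Section 10.4 schedules the comfort questionnaire "After completion of all voids", and step 6.1 agrees: "Once the participant has completed both voids, the participant will be asked to complete the remaining required questionnaire". The form itself (Appendix 6) carries the instruction "After Completion of All Voids". Its first item is "How comfortable was the placement of the PureWick™ External Catheter", its second asks about comfort while voiding, its third is "How comfortable was the removal of the PureWick™ External Catheter", and its fourth asks whether the participant would recommend the device. Each is answered once.

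Protocol Section 11.4.2 plans comfort summaries overall and by gender. SAP Section 2.2.5 is titled "Secondary Endpoint 2 – Overall Comfort Score"; its Table 15 tabulates items such as "How Comfortable was the Placement" in two columns, one per device. SAP Listing 16 shows one row of comfort answers per subject.

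Protocol Section 4.2 describes two settings of interest: where "the external catheter is placed by a healthcare professional as well as in the outpatient or home setting", the latter meaning self or guardian/parent placement.

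**The concern.** By the time the form is completed, the participant has been through two placements and two removals, normally done by different people. Items 1 and 3 speak of one placement and one removal; item 2 covers two voids in the same way. A participant whose two experiences differed has no instruction on whether to rate the first, the last, the worse one or some average.

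If self-placement or self-removal were less comfortable than the HCP's, or the reverse, the comfort data could not show it. Protocol Section 8.2.1 lists discomfort as an anticipated effect for both catheters, and links avoidance of skin injury to how the female device is placed and removed and how the male device is peeled off. The person doing it could therefore plausibly matter. Capture rate and wetness are tabulated by placement in the SAP (Tables 9b and 11); comfort cannot be.

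**Working it through.** The plan states no figure on this point, so the check is a comparison of sections and a count.

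1. **Events against ratings.** Inputs: 40 participants (protocol Section 1.0), two voids each (Section 7.1), one comfort form each (Section 10.4). If everyone completes both voids:
   - placements = 40 × 2 = 80, of which 40 by the HCP and 40 by the participant or guardian/parent; the same holds for removals and for voids;
   - ratings of each item = 40 × 1 = 40, that is, one rating for every two events;
   - ratings attributable to HCP placement = 0 of 40; to self or guardian/parent placement = 0 of 40.

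2. **What one rating can mean.** Suppose a respondent averages the two placements. A score of 3 then fits every (HCP, self) pair that sums to 6: (1,5), (2,4), (3,3), (4,2) and (5,1), which are five different experiences. Suppose instead the respondent answers for one placement only. The form does not record which.

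3. **Can anything else in the data recover it?**
   - Randomised sequence (SAP Listing 2) does not. Every participant has had both placements before the single rating. A difference between sequence groups could be read as a placement effect only if one knew that respondents rate the last event, or the first; averaging would remove the difference altogether.
   - Appendix 6 has no comment field, unlike the low-score prompts on the wetness and IFU forms (Appendices 4 and 7).
   - SAP Table 15 is split by device only, and Listing 16 has no void, placement or comment column.
   - Step 4.7 of Section 10.4 calls for the applicable questionnaires after each void, but the timing table puts comfort after all voids, so it does not bring the form forward.

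4. **Is the split feasible?** The wetness form (Appendix 4) already has separate HCP-placement and self-placement blocks and is given after each void. Applying the same layout to items 1–3 gives 40 × 2 = 80 ratings per item: 40 per placement type, or 20 per placement type within each device.

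5. **Respondent burden.** Now: 4 tick-box items per participant. With the change: 3 × 2 + 1 = 7. Extra: 3 per participant, or 3 × 40 = 120 across the study.

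**The case against.** The strongest reply is that the plan does what it sets out to do. The comfort objective in Section 6.1 concerns comfort after using the device, the endpoint is called an overall score, and Section 11.4.2 promises only overall and by-gender summaries. Summaries by placement are mentioned in Section 11.4.1 for the two primary endpoints alone, and as optional. One rating at the end fits an overall endpoint. This stands. A reader might infer that a planned analysis breaks down or that the secondary endpoint is invalid; the documents do not support that.

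A reader might also infer from Section 4.2 that the study undertakes to compare comfort between settings. It does not. After naming the two settings, the rationale lists what will be collected: capture performance after self-placement, independent or assisted use, and adverse events. Comfort by placement is not on that list. The rationale shows why the split would be useful, not that it was promised.

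Problems specific to self-placement are also partly visible elsewhere. Ease of placement and removal is rated after the self-placed void (Appendix 5). IFU item 3 asks about placing the device on oneself, with comments for low scores (Appendix 7). The HCP records adjustments (step 2.5) and checks the skin after each removal (step 4.4), and irritation is tabulated by placement (SAP Table 6). This lowers the stakes. None of these measures comfort, however, and the ease-of-use and IFU forms have no HCP-placed counterpart from the participant.

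Finally, the study is descriptive, with no hypothesis test (Section 11.0) and no performance goal (Section 6.2), so no decision rule turns on the comfort data. This also stands.

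**Conclusion.** The point holds as a cheap improvement, not as a failure of the plan. Appendix 6 is ambiguous to the respondent on items 1–3, and none of the 40 expected ratings per item can be assigned to HCP placement or to self or guardian/parent placement. Nothing else in either document resolves this, and it cannot be recovered once participants are discharged.

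The consequence is limited to one secondary, descriptive endpoint whose planned summaries do not need the split. The study simply cannot describe comfort separately for the two settings in its rationale. The counts assume that all 40 participants complete both voids; the conclusion does not depend on that, nor on any assumed variability.

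Two limits apply. The second placement is not always the participant's own, so a plain HCP/self split would still mix self-placement with guardian/parent placement. And the absence of a rule for forming the overall comfort score is a separate matter, which changing the timing would neither cause nor cure.

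**What to change.** - **Form (Appendix 6):** ask items 1–3 after each void, in an HCP-placement block and a self-placement block laid out like the wetness form. Keep item 4 (recommendation) once, after both voids.
- **Protocol Section 10.4:** change the comfort row of the timing table and the wording of step 6.1 to match.
- **SAP Table 15:** present items 1–3 by device and placement, as Table 11 does for wetness.
- **SAP Listing 16:** add void and placement columns, and flag voids where a guardian or parent placed the device. The treatment form already asks about guardian/parent help with placement (SAP Section 2.2.1). The SAP shells show no matching item for removal, so one would be needed if removal is to be flagged too.

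The cost is three extra tick-box items per participant, a revised questionnaire, a few table and listing columns, and a protocol change handled under Section 14.0, including IRB review. No extra void, device or visit is needed.

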26.7 Appendix 7 – Participant IFU Evaluation Questionnaire (Both Male and Female)

Participant Number:	Device:					
	 PureWick Male External Catheter					
	 PureWick Flex Female External Catheter					
After Self-Placement Void						
Please respond to the following questions regarding the PureWick™ External Catheter on a scale of 1-5, where 1 is Strongly Disagree, and 5 is Strongly Agree.						
		Strongly Disagree	Disagree	Neutral	Agree	Strongly Agree
	Questions	1	2	3	4	5
1	I was able to understand and follow the written instructions in the PureWick™ External Catheter instructions for use so that I could perform the steps myself.					
1a	If you selected 1, 2 or 3, please provide comments to tell us why you answered as you did (free text).					
2	I was able to understand the pictures in the PureWick™ External Catheter instructions for use so that I could perform the steps myself.					
2a	If you selected 1, 2 or 3, please provide comments to tell us why you answered as you did (free text).					
3	I was able to place the PureWick™ external catheter on myself.					
3a	If you selected 1, 2 or 3, please provide comments to tell us why you answered as you did (free text).					

	Document Type: Global Clinical Title: Clinical Investigation Plan Study ID: UCC-23AC023	Page No: 59 of 59
		Version No: 1.0

Template GFM-10095B

1.0 GENERAL GUIDANCE ON OUTPUT FORMAT

It is suggested that computer-generated output adhere to the following specifications.

1.1 Document Headers and Footnotes

Unless otherwise specified, all computer-generated output should be produced in landscape mode. Required margins: at least 1.25 inches on top (the binding margin [or left for portrait output]), at least 1 inch on right, left, and bottom. All output should have the following header at top of page:

BD	Page n of N
CIP: UCC-23AC023	
Population: Enrolled, PP, ITT, etc.	

And the following as footnote:

Program name: xxxxx.sas	Date DD-MMM-YYYY: hhmmss
Data Source: ADSL, ADTL, ADDEV, ADIMFD, etc.	
Cutoff Date: DD-MMM-YYYY	

1.2 Presentation of Table Numbering and Titles Within Document

Each output should be identified by a numeral followed by the title. The study population should be identified on the line immediately following the title. (example below.)

Table No. Table Title
Table Title continued (if necessary)
Study population

Other general table formatting:

- Column headings should in initial upper-case characters,
- For numeric variables, include “unit” in column heading when appropriate.
- Only these categories for which there are at least one (1) subject represented in one (1) or more groups should be included.
- Footnotes should be single spaced but separated by at least a double space from the bottom line of the table. The notes are aligned vertically by the left vertical border of the table.

 BD	Title: UCC-23AC023 Statistical Analysis Plan Table shells	Page No. 5 of 33
	Study Title: UCC-23AC023 PureWick Adolescent Study CIP/CPSP Version: 1.0	Version No: 1.0

Template GFM-10082B

